8.2 SAFETY ASSESSMENTS & SAFETY PLAN

The NDDI-E standard care depression screening instrument contains a passive suicidality item that has been validated as a suicidality screener.⁷² Tools to notify providers of a positive passive suicidality screen have been implemented in the EHR as part of the study team's prior work and are active at present in the EHR in routine care; these include a pop-up alert to clinicians that typically appears during the clinic visit.⁷³ Tools to evaluate and manage passive suicidality were also developed as part of the study team's prior work and are currently available as well.⁷³ These tools will continue to be available to epilepsy clinicians for all participants since NDDI-E instruments will be completed in the EHR for the EHR arms, and they will be entered into the EHR by study team for REDCap completers prior to the scheduled clinic visit.

To ensure additional safety measures, since study staff will review REDCap-based screening results prior to clinicians and study staff may view EHR based screening results prior to the clinicians, an additional clinician notification process for possible passive suicidality will be in place and will be tracked by the study team.

For screeners completed via the two REDCap-based methods, high urgency email alerts indicating a positive passive suicidality screen will be triggered to the PI and coordinator team members from REDCap (in addition to alerts indicating completion to facilitate entry of results into the EHR). In response to the alerts, the epilepsy clinician will be notified by the study team and these notifications will be tracked. REDCap email alerts based on NDDI-E passive suicidality positive screen are feasible and currently already used by the PI in another collaborative study (*IRB0005120*).

For EHR-arms, automated alerts with NDDI-E results and critical value flag will be sent to the PI and study team as inbasket messages, and study team will notify the epilepsy clinician in a similar manner to the

REDCap-based methods. These additional measures enhance safety by alerting clinicians to high-risk results earlier than occurs at present in standard care practice.

Safety Action Plan Summary:

- **Automated alerts to the PI and study coordinator** from the screener delivery system (REDCap or the EHR) for any positive NDDI-E passive suicidality screens.
- In response to the automated alerts, **PI/study coordinator will notify the treating epilepsy clinician** of the NDDI-E results.
- Next step in management/response to results will be allocated to the treating clinician.
- The study team will track these actions to ensure adherence to this notification plan.

This plan is in addition to actions already implemented during our prior work:

- Pop-up clinician notification in EHR during clinic visits if NDDI-E with potential suicidality [active for all screeners during project, including the REDCap screens when entered in EHR by study team].
- Resources for clinician action to evaluate and manage suicidality: EHR-built smart phrase tool, handouts on suicidality protocol and resources to clinicians posted in clinic and provided prior to study start.

As mentioned above, we have prior experience using automated alerts for screening results in both REDCap and the EHR. Thus, the additional action plan is highly feasible.

Based on our prior work screening >500 consecutive individual patients, we anticipate <5% will require action, and very few if any of these will have active suicidal ideation.

All study procedures will be conducted by appropriately qualified personnel.

Health Insurance Portability and Accountability Act (HIPAA) rules, other relevant federal or state laws, and local institutional requirements will be followed, as applicable.

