6.3 MEASURES TO MINIMIZE BIAS: RANDOMIZATION AND BLINDING

Randomization and blinding. Visits will be randomized 1:1:1:1 to the 4 conditions using blocked randomization to reduce the chance of imbalances, and to help protect against temporal trends. Randomization will be stratified by presence of an existing antidepressant prescription. The randomization table will be prepared with consideration of our previously observed rates of antidepressant prescribing in our epilepsy clinic setting (152 of 536 consecutive screened individuals with epilepsy prescribed an antidepressant). Prior to the start of enrollment, the randomization table will be prepared by the study statistician and submitted to the REDCap developer to put into production. For each visit, the participant's baseline data collection will be completed; activation of the random assignment may then occur. Until that time, the assignment will be concealed to the PI and all other study team members to enhance ***rigor and reproducibility***. The nature of outcome collection prevents study team blinding to allocation for primary outcome ascertainment. Study team will enter instrument results obtained via REDCap into the EHR flowsheets prior to clinic visit (identical EHR location as with EHR allocation). Timely entry is feasible using REDCap email alerts to the study team (method used by PI in prior projects).

The brief consent will have identical wording for all delivery arms to minimize potential bias that could be introduced by the informed consent process related to the different study arm allocations (see sections 5.5 and 10.1.1.1 and 10.1.1.2).

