8 STUDY ASSESSMENTS AND PROCEDURES

8.1 ENDPOINT AND OTHER NON-SAFETY ASSESSMENTS

Baseline demographics and clinical information (including whether there is evidence of an existing antidepressant prescription) will be collected from existing EHR based information using SMART on FHIR REDCap integration. These also include: sex, race, ethnicity, age, diagnoses, zip code, and prescriptions.

Anxiety and depression instruments.

Generalized anxiety disorder-7 (GAD-7)^{68,69} & Neurological Disorders Depression Inventory-Epilepsy (NDDI-E)^{70,71} are well-validated, freely available anxiety and depression instruments that satisfy the American Academy of Neurology Epilepsy Quality Measure for anxiety and depression screening at every visit¹⁴ and are National Institute of Neurological Disorders and Stroke(NINDS) Common Data Elements. Automated EHR-based procedures are already in place for these instruments to be attached as EHR-portal previsit questionnaires and available prior to a scheduled visit for all active adult epilepsy specialty providers at the Wake Forest Comprehensive Epilepsy Center.

AIM 1 Outcomes. Outcomes are determined by the scheduled clinic visit (Table 2), with primary outcome defined as instrument completion prior to visit date/start time. Technical reasons for lack of instrument completion (eg. no patient portal account, no email address available in EHR system, text messages cannot be sent via clinical protocols) will be recorded, but the primary analysis will follow intention to treat principles and include all randomized individuals.

Table 2: Aim 1 Outcomes

Outcome	Source	How obtained?
---------	--------	---------------

Instrument completion (primary)	EHR or REDCap (allocated method)	Review REDCap (REDCap arms) Manual EHR review (EHR arms)
Research team time: sending instruments	REDCap	Start stop timing fields REDCap (seconds)
Research team time: instrument entry (into EHR or REDCap, based on allocation)	REDCap	Start stop timing fields REDCap (seconds)
Patient time from instrument delivery to completion among screening completers	REDCap (and EHR if randomized to EHR)	Send time: study team-activated REDCap timing field at instrument delivery Completion time: review of instrument completion timestamp in EHR or REDCap
Clinic visit completion: visit completed, canceled or patient no-show?	EHR	Manual chart review

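### In the two REDCap arms the staff notification and the EHR pop-up both depend on the same study staff, so a positive suicidality screen submitted with little staffed time left can reach the visit with neither in place

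*Combined protocol and SAP*

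**What the plan says.** Section 8.2 gives two routes by which a positive NDDI-E passive suicidality item reaches the treating clinician.

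**Staff notification.** For the two REDCap arms, "high urgency email alerts indicating a positive passive suicidality screen will be triggered to the PI and coordinator team members from REDCap". Then: "In response to the alerts, the epilepsy clinician will be notified by the study team and these notifications will be tracked". For the two portal arms the automated message also goes to the PI and study team, as an inbasket message, and staff notify the clinician in the same way. In every arm, then, the automated alert stops at the study team.

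**EHR pop-up at the visit.** Section 8.2 says of the existing EHR tools: "These tools will continue to be available to epilepsy clinicians for all participants". The reason given is that portal results are completed in the EHR and that, for the other two arms, "they will be entered into the EHR by study team for REDCap completers prior to the scheduled clinic visit". The summary of the safety plan describes the pop-up as active for all screeners, "including the REDCap screens when entered in EHR by study team". Section 6.3 repeats the commitment ("Study team will enter instrument results obtained via REDCap into the EHR flowsheets prior to clinic visit") and relies on REDCap emails to the study team to make the entry timely.

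**Cut-off for completion.** Section 8.1 describes outcomes as determined by the scheduled visit, "with primary outcome defined as instrument completion prior to visit date/start time".

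**Oversight.** Section 10.1.8 tracks the timeliness and completion of clinician notification for all results that need an alert, with immediate corrective action if a delay is found. Separately, it reviews the timeliness of EHR entry, weekly at first.

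**The concern.** Two safeguards protect a patient only if they can fail separately. In the portal arms they can: if nobody on the study team reads the inbasket message, the pop-up still appears. In the REDCap arms both need a manual act by the same people, prompted by the same email system. A submission may arrive at any moment up to visit start, including a weekend or the minutes before an early appointment. Neither Section 8.2 nor any other section sets a turnaround time, out-of-hours cover or an earlier closing time for the survey.

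At stake is the small group of patients who report possible suicidality too late for staff to act before they are seen. Portal delivery without a reminder is current practice, and there the pop-up would fire. For this group REDCap delivery may give the clinician less warning at the visit than current practice does.

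**Working it through.** **Trace of the two routes.** The plan states no figure on this point, so the check begins with the text.

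| | Portal arms | REDCap arms |
|---|---|---|
| Automated alert goes to | PI and study team | PI and coordinators |
| Clinician notified by | Study team | Study team |
| Result reaches EHR by | Patient's own completion | Staff entry |
| Pop-up needs staff? | No | Yes |
| Stated time limit for staff action | None for notification | Entry before the visit; none for notification |

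An entry deadline of visit start and a completion deadline of visit start cannot both be met for a survey submitted minutes beforehand.

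**Inputs for scale.** From the documents: 220 per arm (Section 9.2), so 2 × 220 = 440 REDCap patients; fewer than 5% expected to need action (Section 8.2). Everything else is assumed: completion of 20%, 40% or 60%; alerts handled Monday to Friday 08:00–17:00; visits hourly 08:00–16:00 on weekdays (45 slots a week); completions uniform over the 168 hours before the visit; a turnaround of T staffed hours.

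**Positives at the 5% ceiling.** 440 × completion × 0.05:
- 20%: 88 × 0.05 = 4.4
- 40%: 176 × 0.05 = 8.8
- 60%: 264 × 0.05 = 13.2

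**Share late.** A completion is late if fewer than T staffed hours remain before visit start. With one visit slot in each of the 45 staffed hours, the average share is T/45:
- T = 1: 1/45 = 2.2%
- T = 8: 8/45 = 17.8%

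A one-minute grid over all slots gives the same values. The risk is concentrated in early visits. For 08:00 appointments the share is 15.2% (T = 1) to 19.4% (T = 8), and for Monday 08:00 it is 38.1% to 42.3%.

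**Expected late positives** (positives × share late), at 20%, 40% and 60% completion:
- T = 1: 0.10, 0.19, 0.29
- T = 8: 0.78, 1.56, 2.35

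**Sensitivity.**
- Alerts read daily 07:00–21:00: 0.6% (T = 1) to 9.4% (T = 8) late. At T = 8 that is 0.41, 0.83 and 1.24 positives.
- Section 2.3.3 says the pop-up waits for an action in the EHR during the visit, so slightly late entry may still work. Allowing 30 minutes' grace gives 1.9% to 17.5%.
- Half of completions in the first 24 hours: 1.3% to 10.4% late, or 0.1 to 0.9 positives at 40% completion.
- Half of completions in the last 24 hours: 6.2% to 47.7% late, or 0.5 to 4.2 positives at 40% completion. Combining the most unfavourable values, with 60% completion and T = 8, gives 13.2 × 0.477 = 6.3.

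**The case against.** The strongest reply is that the plan already covers these patients. The notification duty applies to any positive screen, does not depend on EHR entry and does not lapse when the visit begins. Section 10.1.8 tracks notification itself, not only weekly entry, and promises immediate correction of delays. Most REDCap positives gain from the trial: those handled before the visit reach the clinician sooner, and the plan's claim of "alerting clinicians to high-risk results earlier than occurs at present in standard care practice" is fair for them. Turnaround and cover would ordinarily sit in the quality management plan or Manual of Procedures, which are cited but not among the documents. Section 8.2 also expects very few, if any, of those needing action to have active suicidal ideation.

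Most of this stands, and it keeps the point small. It does not remove it: tracking acts after the event for a patient already seen, and the pop-up's dependence on staff entry is written into Section 8.2.

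A reader might infer more than the documents support:
- *That staff-only alerting is peculiar to the REDCap arms.* It applies to all four; only the loss of an independent pop-up is specific to REDCap.
- *That any out-of-hours positive is missed.* One submitted days ahead is only delayed. Both safeguards are absent only if staff do not act before the visit.
- *That the plan has no provision for a late positive.* It does; what it lacks is a stated time.
- *That Section 5.5 shows staff cannot act on the visit day.* That text concerns approaching patients in clinic for consent. Notifying a clinician needs no staff at the visit.

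The numerical objection also stands. Apart from the 440 and the 5% ceiling, every input is assumed, and eight staffed hours is slow for an alert labelled high urgency.

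**Conclusion.** The point holds as a minor safety matter. In the REDCap arms one unattended mailbox can disable both safeguards, and the assurance that the EHR tools remain available to clinicians for every participant cannot be guaranteed for the latest submissions. The expected number is about 0.1 to 2.4 patients over the trial with weekday staffing and uniform completion timing. It is lower with daily cover and higher if completions cluster in the last day. These figures show scale only, because they rest on assumed hours, turnaround, completion rate and timing. Such a case is a late notification under an existing duty, not an absence of a plan. The primary endpoint is fixed at submission, so neither it nor the comparison between arms is affected. If the quality management plan or Manual of Procedures sets turnaround and cover, what remains is a missing cross-reference.

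**What to change.** In Section 8.2:

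1. Add the treating epilepsy clinician as a direct recipient of the existing high-urgency REDCap alert. The consent text in Sections 5.5 and 10.1.1.2 already tells patients that responses may be shared with their neurology provider.
2. State that a positive arriving too late for EHR entry is communicated directly to the clinician before or during the visit. This is needed alongside the first change, since a clinician in session may not read an email sent minutes earlier.
3. If the quality management plan or Manual of Procedures already sets turnaround and cover, cite it.

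Optionally, existing staff could check REDCap before each clinic session. With checks at 07:30 and 12:30, the late share in the eight-hour case falls from 17.8% to 1.4%. Part of that gain is built in, because the model assumes each check clears every earlier positive by session start. The 07:30 check also falls outside the modelled staffing hours, and it would be recurring work at two sites.

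The required cost is a wording amendment, recording each visit's clinician in REDCap, and at most about 4 to 13 extra messages to clinicians over the trial (4.4 to 13.2 positives at an assumed 20% to 60% completion). The endpoint and its cut-off stay as they are, and the tracking in Section 10.1.8 can show whether the rule works.

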8.3 ADVERSE EVENTS AND SERIOUS ADVERSE EVENTS

N/A as this is not a treatment study.

8.4 UNANTICIPATED PROBLEMS

8.4.1 DEFINITION OF UNANTICIPATED PROBLEMS

This protocol uses the definition of Unanticipated Problems as defined by the Office for Human Research Protections (OHRP). OHRP considers unanticipated problems involving risks to participants or others to include, in general, any incident, experience, or outcome that meets all of the following criteria:

- Unexpected in terms of nature, severity, or frequency given (a) the research procedures that are described in the protocol-related documents, such as the Institutional Review Board (IRB)-approved research protocol and informed consent document; and (b) the characteristics of the participant population being studied;

- Related or possibly related to participation in the research (“possibly related” means there is a reasonable possibility that the incident, experience, or outcome may have been caused by the procedures involved in the research); and
- Suggests that the research places participants or others at a greater risk of harm (including physical, psychological, economic, or social harm) than was previously known or recognized.

8.4.2 UNANTICIPATED PROBLEMS REPORTING

The investigator will report unanticipated problems (UPs) to the reviewing Institutional Review Board (IRB). The UP report will include the following information:

- Protocol identifying information: protocol title and number, PI’s name, and the IRB project number
- A detailed description of the event, incident, experience, or outcome
- An explanation of the basis for determining that the event, incident, experience, or outcome represents an UP
- A description of any changes to the protocol or other corrective actions that have been taken or are proposed in response to the UP

To satisfy the requirement for prompt reporting, UPs will be reported using the following timeline:

- UPs that are serious adverse events (SAEs: life-threatening, require hospitalization, cause persistent or significant incapacity or substantial disruption of ability to conduct normal life functions for >48 hours) will be reported to the IRB and to the study sponsor/funding agency within 24 hours of the investigator becoming aware of the event
- Any other UP will be reported to the IRB and to the funding agency within 7 days of the investigator becoming aware of the problem
- All UPs should be reported to appropriate institutional officials (as required by an institution’s written reporting procedures), the supporting agency head (or designee), and the Office for Human Research Protections (OHRP) within 1 week of the IRB’s receipt of the report of the problem from the investigator

8.4.3 REPORTING UNANTICIPATED PROBLEMS TO PARTICIPANTS

N/A

9 STATISTICAL CONSIDERATIONS

9.1 STATISTICAL HYPOTHESES

Primary Endpoint: AIM 1

Hypothesis: the screening completion proportion will vary across the four modalities tested.

9.2 SAMPLE SIZE DETERMINATION

Sample size and Power. We based our sample size calculation on our primary outcome and hypothesis of a difference in proportions for instrument completion among the 4 groups. With N=220 in each group, we will have statistical power equal to at least 80% to detect an overall difference (two-sided chi-square testing, alpha = 0.05), given a true range among the proportions equal to 0.16 (16%). We believe this range represents a clinically meaningful change in screening rate and would be relevant to sample size calculations for future larger studies.

Our N=880 sample size compares favorably with the typical >1500 visits at Wake Forest Comprehensive Epilepsy Center adult clinics over 6 months, and with our experience during COVID-19-related volume disruptions, when 1097 visits were scheduled and 866 were completed over a 5-month period. Finally, based on our clinic data we expect only a modest decrease in numbers from visits to individuals, and we estimate 923 unique individuals will complete visits over 6 months.

9.3 POPULATIONS FOR ANALYSES

The analysis will follow intention-to treat principles.

9.4 STATISTICAL ANALYSES

9.4.1 GENERAL APPROACH

A pre-specified analysis plan (SAP) will be developed for the primary outcome with additional details on computational specifications, potential covariates, diagnostics, alternative approaches if assumptions are not met, and supportive analyses. A p value of 0.05 will be considered statistically significant.

9.4.2 ANALYSIS OF THE PRIMARY ENDPOINT(S)

We will test our primary outcome and hypothesis of a difference among the 4 proportions for instrument completion using chi-square testing (two-sided, alpha = 0.05). Point estimates for the proportions and corresponding 95% confidence intervals will be used for descriptive purposes. These analyses will follow intention-to-treat principles, and will include all first visits in our target N=880 individuals.

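### Randomisation is stratified by antidepressant prescription but the primary chi-square ignores the stratum; using it is a free, small improvement that pays only if the stratum predicts completion

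*Combined protocol and SAP*

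**What the plan says.** Section 6.3: "Randomization will be stratified by presence of an existing antidepressant prescription". Allocation is blocked, 1:1:1:1. The same section gives the earlier local prevalence of the factor as 152 of 536 and says baseline data are completed before the assignment is activated. Section 8.1 lists the factor among the baseline items taken from the health record ("including whether there is evidence of an existing antidepressant prescription").

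Section 9.2 claims "statistical power equal to at least 80% to detect an overall difference (two-sided chi-square testing, alpha = 0.05"), with 220 per arm and a true range of 0.16 between the proportions. Section 9.4.2 specifies the same test, comparing the four completion proportions "using chi-square testing (two-sided, alpha = 0.05"), with arm proportions and 95% confidence intervals as description. Neither section mentions the stratum.

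Section 9.4.1 promises a later statistical analysis plan with "additional details on computational specifications, potential covariates, diagnostics, alternative approaches if assumptions are not met, and supportive analyses". It names no covariate. Sections 9.4.7 and 9.4.9 do not name antidepressant status as an analysis factor either.

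**The concern.** The team chose one baseline factor to stratify on, and no section carries it into the analysis. Stratified blocking makes the arms nearly equal on that factor, so it contributes almost nothing to the differences between arms. The plain chi-square still uses the pooled variance, which includes the variation between strata. If the factor predicts completion, that variance is too large for the design. The test then rejects less often than 5% under the null and gives up some power.

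Only a little efficiency is at stake. The type I error is not inflated, and the sample size does not depend on this point. A secondary matter is that section 9.4.1 leaves covariates for the primary outcome unnamed. The randomisation stratum is the natural one to fix in advance.

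**Working it through.** **Inputs from the documents.** 220 per arm, range 0.16, alpha 0.05, power at least 80% (section 9.2); stratum prevalence q = 152/536 = 0.2836 (section 6.3).

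**Assumptions, because the documents are silent.** Overall completion p is 0.50, with 0.30 as an alternative. Two arms sit midway between the extremes, which is the least favourable pattern for a given range. The completion gap g between strata runs from 0 to 30 points. The arm effect in percentage points is the same in both strata.

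**1. The plan's own power.** The 3-df noncentrality is n × Σ(pᵢ − p)² / [p(1 − p)].
- At 0.42, 0.50, 0.50, 0.58: 220 × (0.08² + 0.08²) / 0.25 = 220 × 0.0128 / 0.25 = 11.26.
- The critical value is 7.815 and power is 81.4%.
- Away from 0.50 power is higher: 83.1% at a centre of 0.40 or 0.60, and 88.2% at 0.30 or 0.70.
- The smallest n per arm for 80% at centre 0.50 is 213.

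The claim in section 9.2 is correct.

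**2. Share of the variance that lies between strata.** Share = q(1 − q)g² / [p(1 − p)], with q(1 − q) = 0.2836 × 0.7164 = 0.2032. At p = 0.50 and g = 0.20 this is 0.2032 × 0.04 / 0.25 = 3.25%.

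**3. Consequence for the plain test.** With arms balanced within strata, its true type I error is P(χ²₃ > 7.815 / (1 − share)). At g = 0.20 the threshold is 7.815 / 0.9675 = 8.077, which gives 4.44%.

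**4. Consequence for the stratified test.** It keeps the threshold 7.815, and its noncentrality becomes 11.264 / (1 − share). At g = 0.20 this is 11.264 / 0.9675 = 11.64, which gives power of 82.8%. The plain test has the same noncentrality against the threshold 8.077, which gives 81.5%.

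**5. Simulation.** 400,000 trials per setting, permuted blocks of 4 within stratum (block size assumed), p = 0.50, Pearson chi-square against Cochran-Mantel-Haenszel (CMH) general association, both 3 df. The Monte Carlo standard error is about 0.03 points for type I error and 0.06 points for power.

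| Gap (points) | Variance share | Type I error, plain (formula) | Type I error, plain / CMH (simulated) | Power, plain / CMH (simulated) |
|---|---|---|---|---|
| 0 | 0% | 5.00% | 5.0% / 4.9% | 81.6% / 81.6% |
| 5 | 0.20% | 4.96% | 4.9% / 5.0% | 81.7% / 81.8% |
| 10 | 0.81% | 4.86% | 4.9% / 5.0% | 81.8% / 82.1% |
| 15 | 1.83% | 4.68% | 4.7% / 5.1% | 81.8% / 82.5% |
| 20 | 3.25% | 4.44% | 4.4% / 5.0% | 81.8% / 83.1% |
| 30 | 7.31% | 3.79% | 3.8% / 5.0% | 81.9% / 84.8% |

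Formula and simulation agree.

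**6. Other settings.** At p = 0.30 the pattern is the same. Power, plain against CMH, is 88.7% and 89.0% at a 10-point gap, 88.9% and 90.0% at 20, and 89.2% and 91.6% at 30. If the 0.16 range is split two arms against two at p = 0.50, either test has power of at least 98.8%, and the choice hardly matters.

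**The case against.** The strongest reply is that nothing here is wrong. The planned test is valid, it matches the power calculation, and it compares exactly the four raw proportions that will be reported. The benefit depends on a completion gap between strata that the documents do not give; up to 10 points the gain is 0.3 points of power or less. The promised statistical analysis plan already makes room for covariates and supportive analyses. All of this stands, and it is why the point is optional. It does not remove the point, because section 9.4.1 lists topics without committing to any covariate, and section 9.4.2 as written fixes the unadjusted test.

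A narrower objection also has force. Section 6.3 randomises visits, while section 9.4.2 analyses first visits. Repeat visits use up places in the blocks, so balance within strata among first visits is looser than simulated above. If 60% of randomised visits are first visits (an assumed share), simulation puts the plain test's type I error at about 4.6% to 4.7% at a 20-point gap and 4.2% to 4.3% at 30, rather than 4.4% and 3.8%. The power gain stays at about 1.2 and 2.8 points. So the conservatism shown in the table is an upper limit, but the gain remains, and a stratified test also adjusts for any leftover imbalance.

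**Conclusion.** The point holds as a minor refinement. The plan stratifies by a factor that its primary test does not use. The cost of leaving it so is at most slight conservatism and a little lost power: nothing if the factor does not predict completion, about 1 point at a 20-point gap, and about 3 points at 30. These sizes rest on assumed overall completion, assumed gaps and a common arm effect across strata; only the prevalence, the sample size and the range come from the protocol. Validity is not in question, and the stated power holds with either test.

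**What to change.** In section 9.4.2, make the primary test a 3-df Cochran-Mantel-Haenszel general-association test stratified by antidepressant prescription as recorded at randomisation. Logistic regression with arm and stratum, and a 3-df test for arm, is an acceptable alternative; one of the two should be named. Keep the plain chi-square as a sensitivity analysis and the raw arm proportions with 95% confidence intervals as planned. If differences between arms are reported, give stratum-adjusted risk differences.

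If the team prefers to keep the plain chi-square as primary, it should name the stratified test as the supportive analysis in the statistical analysis plan before outcome data are analysed.

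Either route costs one sentence. The factor is already collected before assignment, the test keeps 3 degrees of freedom, and the sample size stays at 880.
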